### 5.2.2 Definition of Dose Limiting Toxicity

DLT's will be defined from toxicities observed during the first cycle of treatment (21 days) for each dose level. See Section 5.2.4 for rules on replacement of subjects in the DLT period.

The occurrence of any of the following toxicities during Cycle 1, if assessed by the Investigator to be possibly, probably or definitely related to study drug (MK-1248 in Arm 1 or the MK-1248 with pembrolizumab combination in Arm 2), will be considered a DLT:

1. Grade 4 non-hematological toxicity (not laboratory)
2. Grade 4 hematological toxicity lasting  $\geq 7$  days, except thrombocytopenia
  - a. Grade 4 thrombocytopenia of any duration
  - b. Grade 3 thrombocytopenia is a DLT if associated with bleeding:
3. Any Grade 3 non-hematological toxicity (not laboratory), with the exception of Grade 3 nausea, vomiting or diarrhea, which will not be considered a DLT unless lasting more than 3 days despite optimal supportive care
4. Any Grade 3 or Grade 4 non-hematological laboratory abnormality, if
  - medical intervention is required, or
  - the abnormality leads to hospitalization, or
  - the abnormality persists for  $>1$  week
5. Febrile neutropenia Grade 3 or Grade 4
6. Any drug-related AE which caused subject to discontinue treatment during Cycle 1
7. Grade 5 toxicity
8. Any treatment-related toxicity which causes a greater than 2 week delay in initiation of Cycle 2

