### 5.2.3 Guidelines for Dose Modification due to Adverse Events

#### 5.2.3.1 Dose Modification and Toxicity Management for Adverse Events Associated with MK-1248 and/or Pembrolizumab

The Common Terminology Criteria for Adverse Events version 4.0 (CTCAE 4.0) must be used to grade the severity of adverse events.

The Investigator may attribute each toxicity event to MK-1248 alone, pembrolizumab alone, or to the combination of both treatments and modify the dose as appropriate. If a dose reduction for toxicity occurs with any agent, the dose may not be re-escalated. Dose modifications are always based on the previous cycle. Reduction or holding of 1 agent and not the other agent is appropriate if, in the opinion of the Investigator, the toxicity is clearly related to one of the study drugs. For subject convenience in Arm 2, if 1 drug is delayed, the second drug can be delayed until both can be administered. If, in the opinion of the Investigator, the toxicity is related to the combination of 2 agents, both drugs should be held according to the recommended dose modification guidelines.

Subjects may have 1 dose modification to MK-1248 throughout the course of the study, as described in [Table 5](#). If further toxicity occurs or the criteria for resuming treatment are not met, the subject must be discontinued from the agent. If a subject experiences several toxicities and there are conflicting recommendations, follow the most conservative dose adjustment recommended (dose reduction appropriate to the most severe toxicity).

Exceptional circumstances to following the dose modification tables below may be considered after consultation with the Sponsor.

Adverse events (both non-serious and serious) associated with MK-1248 and pembrolizumab exposure may represent an immunologic etiology. These adverse events may occur shortly after the first dose to several months after the last dose of treatment.

MK-1248 will be withheld for Grade 3 thrombocytopenia associated with bleeding, Grades 3 and 4 febrile neutropenia, Grade 4 hematological toxicities lasting  $\geq 7$  days, Grade 4 thrombocytopenia of any duration, Grade  $\geq 3$  non-hematological toxicities including laboratory abnormalities, and severe or life-threatening AEs as per [Table 5](#).

Pembrolizumab treatment interruption/discontinuation and toxicity management guidelines are described in Section 5.2.3.2 and Section 5.2.3.3.

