Table 5 MK-1248 Dose Modification and Treatment Discontinuation Guidelines for Drug-Related Adverse Events

Toxicity	Hold Treatment	Criteria for Restarting Treatment	Dose/Schedule for Restarting Treatment	Criteria for Discontinuation after Consultation with Sponsor
Hematological toxicities:				

 
Any Grade 1, 2, or 3 hematological toxicity except Grade 3 thrombocytopenia associated with bleeding and Grade 3 febrile neutropenia
 
	No	N/A	N/A	N/A

 
Grade 3 thrombocytopenia associated with bleeding
 
Grade 3 febrile neutropenia
 
Grade 4 hematological toxicities lasting <math>\geq</math>7 days
 
Grade 4 thrombocytopenia of any duration
 
Grade 4 febrile neutropenia
 
	Yes	Toxicity resolves to Grade 0-1, or to baseline	The dose may be reduced by one dose level upon discussion with Study Team. Intervals between treatments remain unchanged	Toxicity does not resolve within 12 weeks of last dose. Permanent discontinuation should be considered for any severe or life-threatening event
Non-hematological toxicities:				

 
Any Grade 1 non-hematological toxicity
 
Grade 2 alopecia
 
Grade 2 fatigue
 
	No	N/A	N/A	N/A

 
Any Grade 2 non-hematological toxicity except Grade 2 alopecia and Grade 2 fatigue
 
	Consider holding for persistent symptoms	Toxicity resolves to Grade 0-1 or baseline	Clinical AE resolves within 3 weeks: treat at same dose and schedule  Clinical AE does not resolve within 3 weeks: The dose may be reduced by one dose level upon discussion with Study Team. Intervals between treatments remain unchanged	Toxicity does not resolve within 12 weeks of last dose.

 
Any Grade 3 or 4 non-hematological toxicity
 
	Yes	Toxicity resolves to Grade 0-1 or baseline	The dose may be reduced by one dose level upon discussion with Study Team. Intervals between treatments remain unchanged	Toxicity does not resolve within 12 weeks of last dose. Permanent discontinuation should be considered for any severe or life-threatening event

In case toxicity does not resolve to Grade 0-1 within 12 weeks after last infusion, trial treatment should be discontinued after consultation with the Sponsor.

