### **5.2.5 Timing of Dose Administration**

Study treatment may be administered up to 3 days before or 5 days after the scheduled Day 1 of each cycle, beginning in Cycle 3. Cycle 2 Day 1 may be administered up to 5 days after the scheduled day 1. In addition, dosing interruptions are permitted in the case of medical/surgical events or logistical reasons not related to study therapy (e.g., elective surgery, unrelated medical events, subject vacation, and/or holidays). Subjects should be placed back on study therapy within 2 weeks of the scheduled interruption, unless otherwise discussed with the Sponsor. The reason for interruption should be documented in the subject's study record.

In Arm 2, pembrolizumab will be administered first on Day 1 of each cycle, with administration of MK-1248 occurring approximately 30 minutes after completion of the pembrolizumab administration.

Based on preliminary safety information from the ongoing study, the Sponsor recommends that all subjects be prophylactically pre-medicated, 1.5 hours ( $\pm$  30 minutes) before infusion with MK-1248, with the following:

- (1) Dexamethasone, 8 mg intravenously;
- (2) Acetaminophen, 1000 mg orally; and
- (3) Loratadine, 10 mg orally.

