### 7.1.3.1 Laboratory Safety Evaluations (Hematology, Chemistry and Urinalysis)

Laboratory tests for hematology, chemistry and urinalysis are specified in [Table 8](#).

Table 8 Laboratory Tests

Hematology	Chemistry	Urinalysis	Other
Hematocrit	Albumin	Blood	
Hemoglobin	Alkaline phosphatase	Glucose	Serum $\beta$ -human chorionic gonadotropin ( $\beta$ -hCG)
Platelet count	Alanine aminotransferase (ALT)	Protein	Hepatitis HBsAg
WBC (total and differential)	Aspartate aminotransferase (AST)	Specific gravity	Hepatitis C (HCV RNA) or Hepatitis C antibody
RBC	Bicarbonate or carbon dioxide ( $\text{CO}_2$ )	Microscopic exam, if abnormal results are noted	HIV
PT or INR	Calcium	Urine pregnancy test, if required	IgA, IgG, IgM
aPTT	Chloride		Free thyroxine (T4)
	Creatinine		Thyroid Stimulating Hormone (TSH)
	Glucose		Total Triiodothyronine (T3)
	Gamma Glutamyl transpeptidase (GGT)		C reactive protein (CRP)
	Lactate dehydrogenase (LDH)		
	Phosphorus		
	Potassium		
	Sodium		
	Total Bilirubin		
	Direct Bilirubin, if total bilirubin is elevated above the upper limit of normal		
	Total protein		
	Blood Urea Nitrogen		
	Uric Acid		

Laboratory safety tests for screening should be performed within 7 days prior to first dose of study medication. After Cycle 1, predose laboratory tests can be performed up to 72 hours prior to dosing. Results must be reviewed by the investigator or qualified designee and found to be acceptable prior to dosing.

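### Can the same Cycle 1 toxicity be scored as a DLT or not under criterion 8, depending on how Cycle 2 is scheduled?

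*Combined protocol and SAP*

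**What the plan says.** DLT is the primary endpoint (Sections 8.1 and 8.4.2). Section 5.2.2 draws DLTs from "toxicities observed during the first cycle of treatment (21 days) for each dose level". Two of its eight criteria depend on what happens to treatment rather than on grade:

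- Criterion 6: "Any drug-related AE which caused subject to discontinue treatment during Cycle 1".
- Criterion 8: "Any treatment-related toxicity which causes a greater than 2 week delay in initiation of Cycle 2".

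Other sections govern when Cycle 2 is given:

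- **Section 5.2.3.1, one-drug holds.** "Reduction or holding of 1 agent and not the other agent is appropriate if" the investigator considers the toxicity clearly related to one of the drugs. If it is related to the combination, both are held.
- **Section 5.2.3.1, joint scheduling.** "For subject convenience in Arm 2, if 1 drug is delayed, the second drug can be delayed until both can be administered".
- **Table 5, Grade 2 non-hematological events.** Holding MK-1248 is to be considered if symptoms persist, and slow resolution is foreseen: "Clinical AE does not resolve within 3 weeks: The dose may be reduced by one dose level upon discussion with Study Team".
- **Section 5.2.5, dosing window.** "Cycle 2 Day 1 may be administered up to 5 days after the scheduled day 1". Interruptions unrelated to study therapy are also allowed, and the reason must be documented.
- **Section 7.1.3.1, laboratory tests before dosing.** "Results must be reviewed by the investigator or qualified designee and found to be acceptable prior to dosing".

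Section 8.5.1 makes a subject evaluable for DLT after 21 days of observation, or earlier if a DLT occurs. Section 8.6.2 lists DLTs and gives counts for dose levels with at least three subjects.

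**The concern.** Criterion 8 depends on a date that choices unrelated to the toxicity can move. There are three variants.

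1. **Arm 2, one drug held.** A persistent Grade 2 toxicity attributed to MK-1248 keeps that drug off until Day 43. If pembrolizumab is given on Day 22, Cycle 2 has arguably started on time. If pembrolizumab waits for MK-1248, Cycle 2 starts on Day 43. The toxicity and the hold are the same, but the DLT status may differ. The mirror case also exists: Table 6 withholds pembrolizumab for several Grade 2 immune-related events, while Table 5 leaves the MK-1248 hold to judgment.
2. **Both arms, counting origin.** The two weeks could run from the scheduled day or from the end of the 5-day window.
3. **Cycle 2 never starts.** A permanent stop after Day 21 is not literally within Cycle 1 (criterion 6), and no late start exists to measure (criterion 8).

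In each variant the subject stays in the Section 8.5.1 denominator, so only the numerator is in doubt. Longer follow-up before database lock does not resolve a question about a definition. In small cohorts one subject can change the dose decision.

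**Working it through.** **Decision rule that uses the count.** Table 4 gives a = b = 1, k1 = 1, k2 = 1.5 and a 30% target. With x DLTs in n subjects the posterior is Beta(1+x, 1+n−x) with standard deviation SD. The proper-dosing interval is 0.30 − 1.5·SD to 0.30 + 1.0·SD, and the decision follows the interval with the largest posterior probability. With DU assigned when P(rate > 0.30) > 0.95 (an assumed cutoff, which the documents do not state), every Table 4 cell for 0–6 toxicities and n = 4–14 is reproduced. At n = 14:

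| DLTs | Posterior | SD | Interval | P(below) | P(within) | P(above) | Decision |
|---|---|---|---|---|---|---|---|
| 5 | Beta(6,10) | 0.117 | 0.124–0.417 | 0.007 | 0.643 | 0.351 | S |
| 6 | Beta(7,9) | 0.120 | 0.120–0.420 | 0.001 | 0.453 | 0.546 | D |

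**Effect of one subject.** 6/14 − 5/14 = 0.429 − 0.357 = 0.071. P(rate > 0.30) rises from 0.722 to 0.869. In 3+3 cohorts, 0/3 (escalate) becomes 1/3 (expand), and 1/6 (escalate) becomes 2/6 (stop).

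**Calendar.** Cycles last 21 days, so Cycle 2 is scheduled for Day 22 and its window ends on Day 22 + 5 = Day 27. A delay of more than 14 days means a start after Day 36 counted from Day 22, or after Day 41 counted from Day 27. The two counts disagree only for starts on Days 37–41. In variant 1, Day 43 is 21 days after Day 22 and 16 days after Day 27, so the counting origin does not matter there.

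**Variant 2 against the text.** Section 5.2.5 and flow-chart footnote 1 both express the 5 days relative to the scheduled Day 1. The window permits late dosing but does not move the scheduled day. Day 22 is the natural origin, and nothing in the text starts the count on Day 27.

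**Variant 3 against the text.** A related Cycle 1 toxicity that prevents Cycle 2 from ever starting is ordinarily read as delaying it by more than two weeks. Many stops would also be decided within Cycle 1. There are visits on Days 8 and 15, and flow-chart footnote 6 allows predose procedures up to 72 hours early, that is from Day 19. A related stop decided then meets criterion 6. Severe events are mostly DLTs already under criteria 1–5. For Grade 2 events, Table 5 discontinues only if the toxicity has not resolved within 12 weeks of the last dose, well past Day 36.

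**Variant 1 against the text.** The conditions narrow it in turn:

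- The toxicity must be clearly related to one drug. Section 7.2.4 says causality should generally be assigned to the whole regimen, and Section 5.2.3.1 then holds both drugs, so the question of which one starts the cycle falls away.
- The event must escape the other criteria, which leaves mainly Grade 2 toxicities.
- The hold must exceed two weeks.
- The flow chart and Section 4.2.2.4.2 place both drugs on the same day in Cycles 1–4. That pembrolizumab alone would start Cycle 2 is an inference and is stated nowhere.
- Criterion 8 requires that the toxicity cause the delay. That test, with the documented reason for the interruption, gives analysts a basis for separating a toxicity delay from a scheduling choice.

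**The case for a change.** The strongest case for a change is that the endpoint is primary and a one-sentence definition would be cheap. Giving pembrolizumab first (Section 5.2.5) is a dosing order, not a definition of cycle start. The causal test does not fully settle variant 1 either: the second drug waits only because toxicity delayed the first, so one can argue either way about causation. It also leaves open whether an MK-1248 delay alone counts when pembrolizumab was given on time.

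If such events were common, scoring would matter. Suppose a 20% rate of other DLTs and an independent 5–15% rate of events meeting criterion 8 only; both are assumptions, not figures from the documents. The combined rate is 1 − 0.80 × 0.95 = 0.24, up to 1 − 0.80 × 0.85 = 0.32. The 3+3 pass probability, (1−p)³ + 3p(1−p)⁵, falls from 0.709 to between 0.622 and 0.454 if they are counted.

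What stands is that the documents do not say which Arm 2 drug marks the start of Cycle 2. What does not stand is the consequence. The pass probabilities describe escalation decisions, and enrollment has closed. The 5/14 against 6/14 contrast is hypothetical too, because the documents do not show that any dose level reached 14 subjects. The 5–15% rates have no source in the plan.

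**Conclusion.** This is a gap in detail that analysts can fill sensibly, and the plan need not change. No stated rule or figure is shown to be wrong, and asking the sponsor to choose among readings would add a definition without offering a better method. The counting-origin and permanent-stop variants are at most matters of wording. The Arm 2 variant is a genuine but narrow ambiguity, limited to single-drug holds of more than two weeks, mainly for Grade 2 toxicity.

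Its live effect is a possible difference of one subject in a descriptive dose-level DLT count. Section 8.6.2 already requires DLTs to be listed, and each drug's doses are accounted for separately (Section 8.11), so an affected subject can be identified and annotated from data already collected.

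The conclusion rests on three points: enrollment stays closed after 31-Mar-2017, so the count directs no further cohort; affected subjects are few, which is likely but cannot be derived from the documents; and the reasons for delays were documented as Section 5.2.5 asks. It takes no position on how either drug should be held or resumed.

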### 5.2.3 Guidelines for Dose Modification due to Adverse Events

#### 5.2.3.1 Dose Modification and Toxicity Management for Adverse Events Associated with MK-1248 and/or Pembrolizumab

The Common Terminology Criteria for Adverse Events version 4.0 (CTCAE 4.0) must be used to grade the severity of adverse events.

The Investigator may attribute each toxicity event to MK-1248 alone, pembrolizumab alone, or to the combination of both treatments and modify the dose as appropriate. If a dose reduction for toxicity occurs with any agent, the dose may not be re-escalated. Dose modifications are always based on the previous cycle. Reduction or holding of 1 agent and not the other agent is appropriate if, in the opinion of the Investigator, the toxicity is clearly related to one of the study drugs. For subject convenience in Arm 2, if 1 drug is delayed, the second drug can be delayed until both can be administered. If, in the opinion of the Investigator, the toxicity is related to the combination of 2 agents, both drugs should be held according to the recommended dose modification guidelines.

Subjects may have 1 dose modification to MK-1248 throughout the course of the study, as described in [Table 5](#). If further toxicity occurs or the criteria for resuming treatment are not met, the subject must be discontinued from the agent. If a subject experiences several toxicities and there are conflicting recommendations, follow the most conservative dose adjustment recommended (dose reduction appropriate to the most severe toxicity).

Exceptional circumstances to following the dose modification tables below may be considered after consultation with the Sponsor.

Adverse events (both non-serious and serious) associated with MK-1248 and pembrolizumab exposure may represent an immunologic etiology. These adverse events may occur shortly after the first dose to several months after the last dose of treatment.

MK-1248 will be withheld for Grade 3 thrombocytopenia associated with bleeding, Grades 3 and 4 febrile neutropenia, Grade 4 hematological toxicities lasting  $\geq 7$  days, Grade 4 thrombocytopenia of any duration, Grade  $\geq 3$  non-hematological toxicities including laboratory abnormalities, and severe or life-threatening AEs as per [Table 5](#).

Pembrolizumab treatment interruption/discontinuation and toxicity management guidelines are described in Section 5.2.3.2 and Section 5.2.3.3.

Table 5 MK-1248 Dose Modification and Treatment Discontinuation Guidelines for Drug-Related Adverse Events

Toxicity	Hold Treatment	Criteria for Restarting Treatment	Dose/Schedule for Restarting Treatment	Criteria for Discontinuation after Consultation with Sponsor
Hematological toxicities:				

 
Any Grade 1, 2, or 3 hematological toxicity except Grade 3 thrombocytopenia associated with bleeding and Grade 3 febrile neutropenia
 
	No	N/A	N/A	N/A

 
Grade 3 thrombocytopenia associated with bleeding
 
Grade 3 febrile neutropenia
 
Grade 4 hematological toxicities lasting <math>\geq</math>7 days
 
Grade 4 thrombocytopenia of any duration
 
Grade 4 febrile neutropenia
 
	Yes	Toxicity resolves to Grade 0-1, or to baseline	The dose may be reduced by one dose level upon discussion with Study Team. Intervals between treatments remain unchanged	Toxicity does not resolve within 12 weeks of last dose. Permanent discontinuation should be considered for any severe or life-threatening event
Non-hematological toxicities:				

 
Any Grade 1 non-hematological toxicity
 
Grade 2 alopecia
 
Grade 2 fatigue
 
	No	N/A	N/A	N/A

 
Any Grade 2 non-hematological toxicity except Grade 2 alopecia and Grade 2 fatigue
 
	Consider holding for persistent symptoms	Toxicity resolves to Grade 0-1 or baseline	Clinical AE resolves within 3 weeks: treat at same dose and schedule  Clinical AE does not resolve within 3 weeks: The dose may be reduced by one dose level upon discussion with Study Team. Intervals between treatments remain unchanged	Toxicity does not resolve within 12 weeks of last dose.

 
Any Grade 3 or 4 non-hematological toxicity
 
	Yes	Toxicity resolves to Grade 0-1 or baseline	The dose may be reduced by one dose level upon discussion with Study Team. Intervals between treatments remain unchanged	Toxicity does not resolve within 12 weeks of last dose. Permanent discontinuation should be considered for any severe or life-threatening event

In case toxicity does not resolve to Grade 0-1 within 12 weeks after last infusion, trial treatment should be discontinued after consultation with the Sponsor.

With Investigator and Sponsor agreement, subjects with a laboratory adverse event still at Grade 2 after 12 weeks may continue treatment in the trial only if asymptomatic and controlled.

After any Grade 4 drug-related adverse event, subjects should not restart trial treatment without consultation with the Sponsor; the toxicity must have resolved to Grade 0-1 or baseline prior to restarting.

### **5.2.3.2 Dose Interruption/Discontinuation and Toxicity Management Guidelines for Immune-Related Adverse Events Associated with Pembrolizumab**

Adverse events associated with pembrolizumab exposure may represent an immunologic etiology. These irAEs may occur anywhere from shortly after the first dose to several months after the last dose of pembrolizumab treatment and may affect more than one body system simultaneously. Early recognition and initiation of treatment is critical to reduce complications. Based on existing clinical study data, most irAEs were reversible and could be managed with dose interruptions and administration of corticosteroids and/or other supportive care. For suspected irAEs, ensure adequate evaluation to confirm etiology and/or exclude other causes. Additional procedures or tests such as bronchoscopy, endoscopy, and/or skin biopsy may be included as part of the evaluation. Dose interruption/discontinuation and toxicity management guidelines for irAEs associated with pembrolizumab are provided in [Table 6](#).

Table 6 Pembrolizumab Dose Interruption/Treatment Discontinuation and Toxicity Management Guidelines for Immune-Related Adverse Events

General instructions:				
Immune-related AE	Toxicity grade or condition (CTCAEv4.0)	Action taken with pembrolizumab	irAE management with corticosteroid and/or other therapy	Monitor guideline and follow-up
Pneumonitis	Grade 2	Withhold	
 
Administer corticosteroids (initial dose of 1-2 mg/kg prednisone or equivalent) followed by taper
 
	
 
Monitor participants for signs and symptoms of pneumonitis
 
Evaluate participants with suspected pneumonitis with radiographic imaging and initiate corticosteroid treatment
 
Add prophylactic antibiotics for opportunistic infections
 

	Grade 3 or 4, or recurrent Grade 2	Permanently discontinue		
Diarrhea / Colitis	Grade 2 or 3	Withhold	
 
Administer corticosteroids (initial dose of 1-2 mg/kg prednisone or equivalent) followed by taper
 
	
 
Monitor participants for signs and symptoms of enterocolitis (ie, diarrhea, abdominal pain, blood or mucus in stool with or without fever) and of bowel perforation (ie, peritoneal signs and ileus)
 
Participants with Grade <math>\geq 2</math> diarrhea suspicious for colitis should consider GI consultation and performing endoscopy to rule out colitis
 
Participants with diarrhea/colitis should be advised to drink liberal quantities of clear fluids. If sufficient oral fluid intake is not feasible, fluid and electrolytes should be substituted by IV infusion
 

	Grade 4	Permanently discontinue		

Immune-related AE	Toxicity grade or condition (CTCAEv4.0)	Action taken with pembrolizumab	irAE management with corticosteroid and/or other therapy	Monitor guideline and follow-up
AST / ALT elevation or Increased bilirubin	Grade 2	Withhold	
 
Administer corticosteroids (initial dose of 0.5-1 mg/kg prednisone or equivalent) followed by taper
 
	
 
Monitor liver function tests (consider weekly or more frequently) until liver enzyme values return to baseline or are stable
 

	Grade 3 or 4	Permanently discontinue	
 
Administer corticosteroids (initial dose of 1-2 mg/kg prednisone or equivalent) followed by taper
 
	
Type 1 diabetes mellitus (T1DM) or Hyperglycemia	Newly onset T1DM or Grade 3 or 4 hyperglycemia associated with evidence of $\beta$ -cell failure	Withhold	
 
Initiate insulin replacement therapy for participants with T1DM
 
Administer anti-hyperglycemic in participants with hyperglycemia
 
	
 
Monitor participants for hyperglycemia or other signs and symptoms of diabetes
 

Hypophysitis	Grade 2	Withhold	
 
Administer corticosteroids and initiate hormonal replacements as clinically indicated
 
	
 
Monitor for signs and symptoms of hypophysitis (including hypopituitarism and adrenal insufficiency)
 

	Grade 3 or 4	Withhold or permanently discontinue		
Hyperthyroidism	Grade 2	Continue	
 
Treat with non-selective beta-blockers (eg, propranolol) or thionamides as appropriate
 
	
 
Monitor for signs and symptoms of thyroid disorders
 

	Grade 3 or 4	Withhold or permanently discontinue		
Hypothyroidism	Grades 2-4	Continue	
 
Initiate thyroid replacement hormones (eg, levothyroxine or liothyroinine) per standard of care
 
	
 
Monitor for signs and symptoms of thyroid disorders
 

Nephritis and Renal dysfunction	Grade 2	Withhold	
 
Administer corticosteroids (prednisone 1-2 mg/kg or equivalent) followed by taper
 
	
 
Monitor changes of renal function
 

	Grade 3 or 4	Permanently discontinue		
Myocarditis	Grade 1 or 2	Withhold	
 
Based on severity of AE, administer corticosteroids
 
	
 
Ensure adequate evaluation to confirm etiology and/or exclude other causes
 

	Grade 3 or 4	Permanently discontinue		

Immune-related AE	Toxicity grade or condition (CTCAEv4.0)	Action taken with pembrolizumab	irAE management with corticosteroid and/or other therapy	Monitor guideline and follow-up
All other immune-related AEs	Intolerable/persistent Grade 2	Withhold	

Based on type and severity of AE, administer corticosteroids

	

Ensure adequate evaluation to confirm etiology and/or exclude other causes

	Grade 3	Withhold or permanently discontinue based on the type of event. Events that require discontinuation include but are not limited to: Gullain-Barre Syndrome, encephalitis		
	Grade 4 or recurrent Grade 3	Permanently discontinue		

1. The decision to withhold or permanently discontinue pembrolizumab is at the discretion of the investigator or treating physician.

**NOTE:** For participants with Grade 3 or 4 immune-related endocrinopathy where pembrolizumab is withheld, pembrolizumab may be resumed when AE resolves to Grade  $\leq 2$  and is controlled with hormonal replacement therapy, or metabolic control is achieved (in case of T1DM).

